9.9 Prohibited Concomitant Medication

Due to their potential effect on cough reflex sensitivity, the use of opioids, dextromethorphan, gabapentin, pregabalin, baclofen, antihistamines or tricyclic antidepressants (e.g. amitriptyline) for treatment of cough is not allowed throughout the study. Subjects must have discontinued these drugs at least 1 month prior to Screening and should not have them started during the study. Subjects may, however, be permitted to continue to use these drugs if they have been prescribed solely for the management of another disorder (eg neuropathic pain, depression).

The use of other drugs taken solely for the treatment of cough (including those used on an as needed basis) is also prohibited from at least 1 month prior to Screening.

[REDACTED]

[REDACTED]

A horizontal bar chart showing the distribution of 1000 samples across 10 categories. The categories are represented by horizontal bars of varying lengths. The x-axis is labeled with 'Category' and 'Count' (1-10). The y-axis is labeled with 'Sample' (1-1000).

Category	Count
1	100
2	100
3	100
4	100
5	100
6	100
7	100
8	100
9	100
10	100

9.10 Other Study Restrictions

For more information, contact the Office of the Vice President for Research and Economic Development at [contact] or [contact].

10. STUDY SCHEDULE

Table 1: Schedule of Events

	Screening Day -21 to 1 ^j	Baseline / Day 1	Wk 2 (± 3 days) ^k	Wk 4 (± 3 days) ^k	Wk 8 (± 5 days) ^k	Wk 12 (± 5 days) ^k	Early Termination	Wk 14 follow-up (± 5 days) ^k
Informed Consent	X							
Medical History	X							
Physical Examination ⁱ	X	X ^c					X	X
Spirometry	X							
Incl/Excl Criteria	X	X ^c						
Randomization		X						
Vital Signs ^a	X	X ^c	X	X	X	X	X	X
12-lead ECG	X	X ^c	X	X	X	X	X	X
Ambulatory cough monitoring ^b	X ^g		X	X		X		
LCQ		X ^c	X	X	X	X		
Global Rating of Change			X	X	X	X		
Cough Severity VAS		X ^c	X	X	X	X		
Urge-to-Cough VAS		X ^c	X	X	X	X		
PK sample			X ^h	X ^h	X ^h	X ^h		
Safety labs ^e	X	X ^c		X ^h	X ^h	X ^h	X	X
Opiate drug screen		X ^c	X ^h	X ^h	X ^h	X ^h		
Pregnancy test ^f	X	X ^c		X	X	X	X	X
Dosing ^d		X -----			X -----			
AE recording		X -----				X -----		
Con Med recording		X -----				X -----		

^a Vital signs: systolic and diastolic blood pressure, pulse, temperature; weight (weight at Baseline/Day 1, Week 12 and Follow-up only)

^b ACM [REDACTED] to be fitted during the visit and initiated prior to the subject leaving the clinic, monitoring will be continuous for 24hrs and device switched off after this period. Subjects will either return the ACM to the clinic (during Screening this must be done the following day) or collection from the subjects will be organized

^c Performed prior to start of dosing

^d Subjects are given their first dose of IMP in the clinic. All doses to be taken at approximately the same time each day; on clinic visits subjects will take their dose in the clinic after the pre-dose PK and safety samples, as applicable, have been taken. All other assessments can be performed post-dose

^e Safety labs include blood samples and urine samples

^f Pregnancy test in women of child-bearing potential only; serum pregnancy test at Screening, urine pregnancy at Baseline/Day 1, Wks 4, 8, and 12

g If the ACM fails during the Screening assessment and no useable recording is generated, the 24hr Screening ACM may be repeated and in this circumstance the Screening period may be extended by up to 1 week (to a maximum of 28 days)

h All blood and urine samples are taken immediately prior to the dose

i Full physical examination at Screening; symptom directed physical examination at subsequent visits

j Screening period may be extended for up to 1 week should the original ACM fail and this need to be repeated

k All visits and visit windows relate to Day 1

10.1 Volume of Blood sampling

Approximate blood sample volumes are detailed below. The volumes for individual samples may vary accordingly to laboratory requirements and the number of samples taken may increase due to unscheduled visits, lost or damaged samples where additional blood draws are needed, however, the total volume is not expected to exceed 150 mL per subject

Clinical chemistry	5 mL
Hematology	3 mL
PK	6 mL

10.2 Efficacy assessments

10.2.1 Ambulatory Cough Monitor

Subjects will be fitted with an ACM [REDACTED] to record objective cough frequency over 24 hours at the Screening, Weeks 2, 4, and 12 Visits.

The ACM will be initiated prior to the subject leaving the clinic to monitor cough frequency over 24 hours. After this period, the subjects will either return the ACM to the clinic (during Screening this must be done the following day) or collection from the subjects will be organized; and the cough frequency will be determined.

The digitally recorded data from the ACM will be forwarded to [REDACTED] who will undertake cough counting for all subjects using a standardised process.

The awake period is considered to be the time between subjects rising from their beds in the morning and retiring to their beds in the evening. This can be determined from the 24-hour acoustic recordings and approximates to waking hours when cough rates are highest. Analysed data will be transferred to [REDACTED] for statistical analysis. [REDACTED] will be provided with subject identifier information but will not have access to the randomisation code.

10.2.2 Leicester Cough Questionnaire

The LCQ is a 19-item questionnaire that assesses cough-related Quality-of-Life. It has three domains (physical, psychological and social). The total score range is 3-21 and domain scores each range from 1-7; a higher score indicates a better Quality-of-Life.

Subjects will complete the LCQ whilst in the clinic at Baseline/Day 1 (pre-dose), Weeks 2, 4, 8, and 12.

10.2.3 Cough Severity Visual Analogue Scale

The cough VAS is a 100-mm scale on which subjects indicate the severity of cough in the previous 24 hours, both during the daytime (awake time) and during night-time (non-awake time) separately. The VAS ranges from “no cough” on the left to “worst cough” on the right.

Subjects will complete the cough severity VAS at Baseline/Day 1, Weeks 2, 4, 8, and 12.

10.2.4 Urge-to-Cough

The Urge-to-Cough VAS is a 100-mm scale on which subjects indicate their Urge-to-Cough over the previous 24 hours (day/awake time and night time combined). The VAS ranges from “no Urge-to-Cough” on the left to “severe Urge-to-Cough” on the right.

Subjects will complete the Urge-to-Cough VAS at Baseline/Day 1, Weeks 2, 4, 8, and 12.

10.2.5 Global Rating of Change Questionnaire for Cough Frequency and Severity

In the Global Rating of Change Scale subjects will indicate if there has been a change in their symptoms (cough frequency and, separately, cough severity) since starting the IMP. They will respond with “worse”, “about the same” or “better”. If they indicate a change (either “worse” or “better”) they will then further indicate on a 7-point scale the degree of change ranging from 1 (almost the same, hardly any change) to 7 (a very great deal changed).

Subjects will document their Global Rating of Change in Cough Frequency and Cough Severity at Weeks 2, 4, 8, and 12.

10.3 Safety Assessments

10.3.1 Medical history and concomitant diseases

A review of medical and medication history will be performed at Screening to confirm subject eligibility. This must be confirmed by an investigator.

- The investigator must record all medically and clinical relevant information regardless of the time since the date of diagnosis

History should include (but is not limited to):

- All current and past medications taken during three months before the Screening Visit
- Relevant history of respiratory, cardiovascular, renal, gastro-intestinal, hepatic, endocrine, hematological, neurological, psychiatric and any other diseases
- The specific history related to diagnosis of CRC according to either the ACCP guidelines (for subjects at US sites) or the BTS guidelines (for subjects at UK sites). Evidence of diagnosis (i.e. exclusion of other etiology) will be documented in the source data.

10.3.2 Physical examinations

A full physical examination will be conducted at the Screening visit and a symptom directed physical examination at the time points indicated in the Study Schedule in Table 1: Schedule of Events. This will be completed by a physician or an appropriately qualified delegate.

A full physical examination is composed of a review of the following body systems:

- General appearance
- Skin
- Head, eyes, ears, nose and throat
- Respiratory
- Cardiovascular
- Abdomen (including liver and kidneys)
- Musculoskeletal
- Neurological

Any abnormalities that are identified at the Screening Visit will be documented on the medical history eCRF page. Any changes (including new and worsening findings) between the Screening Visit and Final study visit should be captured as AEs on the AE eCRF page, as determined by the Investigator and documented in the subject's notes.

If an improvement/resolution of a physical examination finding documented in the subject's medical history occurs during the study, it should be recorded in the source document. If there is resolution of a physical examination finding previously noted as an AE, then the event resolution and stop date should be recorded on the AE eCRF page and documented in the subject's notes.

10.3.3 Spirometry

Spirometry measurements will be conducted in accordance to local practice, adjusting for race, gender and age. For patients of mixed race, the "predominant race" as self-reported by the patient will be used and if this is not possible to determine, the predicted values for Caucasians will be used.

Spirometry will be performed at the Screening visit. The highest values (FEV₁ and FVC) from three technically satisfactory attempts will be recorded and used for the purpose of eligibility.

10.3.4 12-Lead ECGs

Resting 12-lead ECG data will be captured at all study visits, as indicated in Table 1: Schedule of Events.

All ECGs will be performed after the patient has rested for five minutes in a semi-recumbent position. The same model of ECG recorder will be used throughout the study for any given subject.

All ECG reports must be reviewed, signed and dated by the Investigator or delegated physician. Reports will then be filed with the subject's medical record. The Investigator will comment on all abnormal findings and determine whether they are clinically significant. These assessments will be recorded in the eCRF and clinically significant findings must also be reported as AEs in the eCRF.

10.3.5 Clinical chemistry

Blood for clinical chemistry assessments will be collected as indicated in the Study Schedule in Table 1: Schedule of Events and sent to a central laboratory for analysis. The following clinical chemistry parameters will be assessed: sodium, potassium, glucose, urea, creatinine, creatine kinase, albumin, calcium, phosphate, bilirubin (total), alkaline phosphatase, aspartate transaminase (AST), alanine transaminase (ALT), gamma glutamyl transferase (GGT), bicarbonate, magnesium, chloride, total protein. Subjects do not need to fast before clinical chemistry samples are taken.

All clinical chemistry test reports must be reviewed, signed and dated by the Investigator or delegated physician. Reports will then be filed with the subject's medical record. The Investigator will comment on all abnormal results and determine whether they are clinically significant. Clinically significant findings must also be reported as adverse events in the eCRF.

10.3.6 Hematology

Blood for hematology assessments will be collected as indicated in the Study Schedule in Table 1: Schedule of Events and sent to a central laboratory for analysis. The following hematology parameters will be assessed: red blood cell (RBC) count, white blood cell (WBC) count, hematocrit, hemoglobin, MCV, platelet count and WBC differentials.

All hematology test reports must be reviewed, signed and dated by the Investigator or delegated physician. Reports will then be filed with the subject's medical record. The Investigator will comment on all abnormal results and determine whether they are clinically significant. Clinically significant findings must also be reported as adverse events in the eCRF.

10.3.7 Urinalysis

Urine for urinalysis assessments will be collected as indicated in the Study Schedule in Table 1: Schedule of Events and sent to a central laboratory for analysis. Urinalysis will include glucose, bilirubin, ketones, specific gravity, blood, pH, protein, urobilinogen, nitrites, leucocyte esterase, sedimentation.

All urinalysis test reports must be reviewed, signed and dated by the Investigator or delegated physician. Reports will then be filed with the subject's medical record. The Investigator will comment on all abnormal results and determine whether they are clinically significant. Clinically significant findings must also be reported as adverse events in the eCRF.

A urine sample will also be collected to perform the opiate drug screen.

10.3.8 Vital signs

Vital signs will be measured at the time points indicated in Table 1: Schedule of Events and will include systolic and diastolic BP, pulse, temperature and weight. Weight will be measured at Baseline/Day 1, Week 12 and Follow-up only.

Blood pressure will be measured using a standardized process:

- Subject should sit for ≥ 5 minutes with feet flat on the floor and measurement arm supported so that the midpoint of the manometer cuff is at heart level
- Use an automatic blood pressure device with an appropriately sized cuff with the bladder centered over the brachial artery
- Measure and record the blood pressure using the same arm throughout the study

All measurements are to be recorded on the Vital Signs eCRF.

All vital signs must be reviewed by the Investigator or delegated physician. The Investigator will comment on all abnormal results and determine whether they are clinically significant. These assessments will be recorded in the eCRF and clinically significant findings must also be reported as adverse events in the eCRF.

10.3.9 Pregnancy Testing, Contraception and Pregnancy

10.3.9.1 Pregnancy Testing

Female subjects of childbearing potential (WOCP) will have a serum pregnancy test at initial Screening to confirm a negative result for subject eligibility, and a dipstick urine pregnancy test will be performed at Baseline/Day1 and must be negative for the subject to remain eligible. A dipstick urine pregnancy test will be performed at Weeks 4, 8 12, and 14. Tests must be negative for the subject to continue with dosing.

10.3.9.2 Contraception

Female subjects of childbearing potential and male subjects with female partners of childbearing potential must follow the permitted contraceptive methods outlined in Section 7.2 for the duration of their participation in the study.

Male subjects will also be reminded to continue to use the permitted contraception methods for 90 days following discontinuation of IMP.

10.3.9.3 Pregnancy

The Investigator will collect pregnancy information on any female subject who becomes pregnant while participating in this study and for up to 30 days after the last dose of IMP. The Investigator will record pregnancy information on the appropriate form and submit it to the Medical Monitor within 24-hours of learning of a subject's pregnancy through the same process as reporting an SAE. The subject will also be followed to determine the outcome of the pregnancy. Information on the status of the mother and child will be forwarded to the Medical Monitor. Generally, follow-up will be no longer than six to eight weeks following the estimated delivery date. Any premature termination of the pregnancy will be reported.

Female subjects will be instructed that if they become pregnant during the study or up to 30 days after their last dose of IMP, this should be reported to the investigator. The investigator should also be notified of pregnancy occurring during the study but confirmed after completion of the study.

Any female subject reporting a pregnancy during the study will be withdrawn from the study.

If the partner of a male study subject becomes pregnant during the subject's participation in the study and for up to 90 days after the last dose of IMP, this should be reported to the investigator. Consent will be sought from the partner and, if granted, any pregnancy will be followed and the status of mother and/or child will be reported to the sponsor after delivery.

10.4 Pharmacokinetics

Blood samples for analysis of plasma orvepitant concentrations will be collected at the clinic visits at Weeks 2, 4, 8 and 12, immediately prior (<15 mins) to the dose to be taken in the clinic.

The actual date and time of each blood sample collection will be recorded, together with the date and time of the most recent dose of IMP.

Approximately 6 mL of blood will be collected at each time point. Details of PK blood sample collection (including volume to be collected), processing, storage and shipping procedures will be provided in the Study Manual.

10.5 Adverse events

10.5.1 Definitions

Adverse Event (AE)

Any untoward medical occurrence in a subject or clinical trial subject administered a IMP and which does not necessarily have a causal relationship with this treatment. An AE can therefore be any unfavorable and unintended sign (including an abnormal laboratory finding, for example), symptom, or disease temporally associated with the use of a IMP, whether or not considered related to the IMP.

Adverse Drug Reaction (ADR)

All AEs considered to be untoward and unintended responses to a IMP related to any dose should be considered ADRs. The definition covers also medication errors and uses outside what is foreseen in the protocol, including misuse and abuse of the product. The phrase “responses to a IMP” means that a causal relationship between a IMP and an AE is at least a reasonable possibility, i.e., the relationship cannot be ruled out.

Serious Adverse Event (SAE)

An adverse event that:

- Results in death
- Is life-threatening (i.e. the subject was at risk of death at the time of the event; it does not refer to an event which hypothetically might have caused death if it was more severe)
- Requires in-subject hospitalization or prolongation of existing hospitalization (see explanation below)
- Results in persistent or significant disability/incapacity
- Is a congenital anomaly/birth defect
- Is considered to be an important medical event

Based upon medical and scientific judgment, important medical events that may not be immediately life-threatening, or result in death or hospitalization, but may jeopardize the subject or may require intervention to prevent one of the other outcomes listed in the definition above may be considered a SAE.

Hospitalizations are defined as initial or prolonged admissions that include an overnight stay. Hospitalization or prolonged hospitalization for technical, practical or social reasons, in the absence of an adverse event is not an SAE and neither is attendance at an Emergency Room / Accident and Emergency Department that takes place in the evening or night and does not result in admission to the hospital.

Pregnancy

Pregnancy itself is not considered an AE. However, any pregnancy complication, spontaneous or elective abortion (for medical reasons), still birth, neonatal death, or congenital anomaly will be recorded as an AE or SAE.

Unexpected Adverse Drug Reaction

An adverse reaction, the nature or severity of which is not consistent with applicable product information (e.g., IB for an unapproved IMP).

Reports which add significant information on the specificity, increase of occurrence, or severity of a known, already documented serious adverse reaction constitute unexpected events.

Suspected Unexpected Serious Adverse Reaction (SUSAR)

A serious adverse event that is suspected to be related to the administered medicinal product and the nature or severity of which is not consistent with applicable product information.

10.5.2 Assessment of Severity

The severity (intensity) of each adverse event will be classified as:

- **Mild** Awareness of sign or symptom, but easily tolerated
- **Moderate** Sign or symptom causes discomfort, but does not interfere with normal activities
- **Severe** Sign or symptom of sufficient intensity to interfere with normal activities

10.5.3 Assessment of Causality

A determination will be made of the relationship (if any) between an AE and the study drug. A causal relationship is present if a determination is made that there is a reasonable possibility that the AE may have been caused by the drug or study procedure. AEs will be classified as either related or unrelated.

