11.6 Statistical Methods for Safety Parameters

Safety data will be summarised descriptively for each treatment group. No formal inferential tests will be performed on safety data.

The number of treatment emergent AEs (TEAEs), and subjects with TEAEs, will be compared between groups. TEAEs are defined as AEs that first occurred or worsened in severity after the first dose of IMP.

TEAEs will be summarised for all causality AEs and for treatment-related AEs (those with related relationship to IMP and missing). TEAEs will be summarised by MeDRA body system and preferred term. TEAEs will also be reported by severity.

Any deaths, SAEs and AEs leading to discontinuation of IMP administration will also be summarised by treatment group.

SAEs will be presented in a similar way to AEs.

Vital signs will be summarised for each treatment group by visit. Summary statistics will be presented for absolute values and the change from Baseline.

ECGs will be assessed by the Investigator for abnormal findings. These will be categorised and summarised as normal, abnormal-not clinically significant or abnormal-clinically significant. ECG intervals will be recorded and summarised as absolute values and changes from Baseline.

Clinical laboratory data for individual subjects will be listed and any out of range values will be highlighted. Laboratory data will be summarised for each treatment group by visit. Summary statistics will be presented for absolute values and change from Baseline, as well as an analysis of shifts from Baseline.

Extent of exposure and compliance will be evaluated.

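### Section 10.5.3 merges drug and study-procedure causation into one related/unrelated label, while the safety definitions and the treatment-related TEAE table need relationship to IMP alone

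*Protocol*

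**What the plan says.** Section 10.5.3 consists of three short statements on causality. The first sets the question: "A determination will be made of the relationship (if any) between an AE and the study drug". The second sets the criterion for a causal relationship, and the third allows one binary answer. Together they require a "reasonable possibility that the AE may have been caused by the drug or study procedure. AEs will be classified as either related or unrelated".

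Three other places depend on a causality judgement:

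- Section 10.5.1 defines an ADR as a response to the IMP, and a SUSAR as "A serious adverse event that is suspected to be related to the administered medicinal product" whose nature or severity does not fit the product information. Neither definition mentions procedures.
- Section 10.5.4 has the investigator give a first causality opinion with every SAE report, and points to Section 10.5.3 for how to form it.
- Section 11.6 plans two TEAE summaries: "TEAEs will be summarised for all causality AEs and for treatment-related AEs (those with related relationship to IMP and missing". The time restriction is by onset: "TEAEs are defined as AEs that first occurred or worsened in severity after the first dose of IMP".

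The protocol describes no separate classification for relationship to a study procedure.

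**The concern.** The question asked in 10.5.3 is about the drug, but the test for answering yes is about the drug or a procedure, and the answer is a single binary label. Section 11.6 needs a variable, relationship to IMP, that this rule does not produce. Under the written criterion, a bruise from venepuncture or a skin reaction to the cough monitor has to be marked related, and nothing in the protocol then separates it from a suspected drug reaction.

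This is an instruction on how investigators judge and record each event. A statistical analysis plan cannot recover a distinction that was never collected, so the matter belongs in the protocol.

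Safety and tolerability of the three doses against placebo is a stated secondary objective (Section 6.2), and Section 5.4 says the study is meant to identify a dose for Phase 3. The treatment-related table is one of the descriptive summaries serving that objective. It should show what its title says.

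**Working it through.** The protocol states no figure on this point, so there is none to reproduce. The check is a comparison of text, followed by a count of opportunities and a conditional illustration.

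**1. What each place requires**

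| Section | Relationship required |
|---|---|
| 10.5.3, first sentence | study drug |
| 10.5.3, criterion | drug or study procedure |
| 10.5.3, categories | one label, related or unrelated |
| 10.5.1, ADR | IMP |
| 10.5.1, SUSAR | administered medicinal product |
| 10.5.4, SAE causality | whatever 10.5.3 gives |
| 11.6, treatment-related TEAEs | IMP (or causality missing) |

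The 10.5.3 criterion is the only entry that admits procedures, and it is the one that tells the investigator when to mark an event related. From a label meaning drug or procedure, the subset meaning drug cannot be derived. The conflict therefore lies both inside 10.5.3 and between 10.5.3 and its users.

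**2. Opportunities after the first dose (Table 1, completing subject)**

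- Blood draws at Weeks 2, 4, 8, 12 and 14: 5.
- 12-lead ECGs at Weeks 2, 4, 8, 12 and 14: 5.
- 24-hour cough monitoring at Weeks 2, 4 and 12: 3.

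The TEAE restriction removes events that begin during Screening, unless they worsen after dosing. It does not remove events from these later procedures. The schedule is the same in all four arms.

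**3. Form of the effect if only one label is recorded**

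Let d be the proportion of subjects with a drug-attributed AE in an arm and p the proportion with a procedure-caused AE. Take p as the same in every arm and independent of d. The tabulated proportion is 1 − (1 − d)(1 − p). The difference between active and placebo becomes (d_active − d_placebo)(1 − p).

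The protocol gives neither d nor p. With d assumed at 10% on active and 5% on placebo, and p assumed between 0% and 10%:

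| p (assumed) | Active | Placebo | Difference | Ratio |
|---|---|---|---|---|
| 0% | 10.0% | 5.0% | 5.0 points | 2.0 |
| 5% | 1 − 0.90 × 0.95 = 14.5% | 1 − 0.95 × 0.95 = 9.75% | 4.75 points | 1.49 |
| 10% | 1 − 0.90 × 0.90 = 19.0% | 1 − 0.95 × 0.90 = 14.5% | 4.5 points | 1.31 |

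These rows show the direction and shape only. Attributed rates rise in both arms, the ratio moves toward 1, and the risk difference barely changes.

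**The case against.** The strongest reply is that Section 11.6 already says relationship to IMP. A reader might infer from 10.5.3 that the analysis will report every AE marked related as treatment-related. The text does not say that. On paper, a procedure-only event does not belong in the table. The first sentence of 10.5.3, the ADR and SUSAR definitions and 11.6 are all drug-specific, so the mention of procedures can be read as one loose phrase. This part of the reply stands, and it limits the point to an inconsistency with a possible consequence. It does not remove the point, because 11.6 still asks for something that the only defined classification cannot deliver.

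A second reply is that misclassification depends on forms not shown. The eCRF or SAE form may hold a separate procedure field, and Section 10.5.4 leaves detailed SAE instructions to a Study Manual. That is correct, and it is why the consequence is stated conditionally. A form should nevertheless follow the protocol's criterion and not have to correct it.

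A third reply is that little turns on the label. Safety data are summarised descriptively without hypothesis tests. All-causality TEAEs, severity, deaths, SAEs and AEs leading to discontinuation do not depend on it. This also stands: only the treatment-related subset and the SAE causality opinion are exposed.

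A reader might also infer a threat to the blind, with a procedure-caused SAE handled as a SUSAR and unblinded under Section 9.7. That route is remote. The event would have to be serious, unexpected, and treated as suspected to be related to the product despite the definition in 10.5.1. Section 9.7 then unblinds only the subject concerned and sends investigators a blinded copy.

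**Conclusion.** The point holds as an internal inconsistency that is wrong as written. Section 10.5.3 defines relatedness by drug or procedure with one label, while 10.5.1 and 11.6 require relatedness to IMP and 10.5.4 passes the 10.5.3 rule on to SAE reports.

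If the forms carry only that label, post-dose procedure-caused AEs would enter the treatment-related table in all arms and raise the attributed rates, placebo included. No directional bias between arms is expected, given the common schedule and blinded assessment. The size cannot be calculated from the protocol, and the illustrative ratios above rest on assumed rates and should not be quoted as estimates. It would also go too far to say that the comparison of active with placebo is materially diluted: in the illustration the risk difference falls only from 5.0 to between 4.75 and 4.5 points. The protocol does not say that the Phase 3 dose choice rests on this table.

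**What to change.** In Section 10.5.3, remove study procedures from the criterion for relationship to IMP, so that it matches the section's first sentence. Add a separate yes/no item for relationship to a study procedure. State in Section 11.6 that treatment-related TEAEs use the IMP item only, and in Sections 10.5.1 and 10.5.4 that SUSAR assessment does the same.

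The cost is a protocol wording change and, if the forms lack it, one extra item on the eCRF and SAE form. Section 11.1 reports that the first sample size review is complete, so subjects have already been followed under the present rule. AEs already marked related would need a query, answered while treatment remains blinded, to assign drug, procedure or both. If the forms already separate the two, only the wording needs to change.
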